Statistical methods	Data will be statistically analysed using GraphPad Prism v10.1.2 (La Jolla, USA). Outcomes will be tested for significant within-group and between-group differences in pre-intervention and post-intervention means using two-way analysis of variance (ANOVA). Additionally, mean change in outcomes will be tested for statistical significance between the two groups using the independent samples t-test (or non-parametric alternative if data are not normally distributed).

ABBREVIATIONS

ABCD	Association of British Clinical Diabetologists
ACCP	American College of Chest Physicians
AE	Adverse Event
ANOVA	Analysis of variance
AT	Aerobic threshold
ATS	American Thoracic Society
BIA	Bioimpedance analysis
BMI	Body mass index
CI	Chief Investigator overall
COMAP	Centre Of Metabolism, Ageing & Physiology
COPD	Chronic obstructive pulmonary disease
CPET	Cardiopulmonary exercise test
CRF	Case Report Form
CV	Curriculum vitae
DMC	Data Monitoring Committee
ECG	Electrocardiogram
ELISA	Enzyme-linked immunosorbent assay
EMG	Electromyography
GCP	Good Clinical Practice
HbA1c	Glycated haemoglobin
HIIT	High-intensity interval training
HRA	Health Research Authority
HR _{max}	Maximum heart rate
ICF	Informed Consent Form
IVGTT	Intravenous glucose tolerance test
LCD	Low calorie diet

NHS	National Health Service
PI	Principal Investigator at a local centre
PIS	Participant Information Sheet
PTR	Path to Remission
REC	Research Ethics Committee
R&D	Research and Development department
SAE	Serious Adverse Event
SD	Standard deviation
T2D	Type 2 diabetes
VLCD	Very-low calorie diet
VO _{2max}	Maximum rate of oxygen consumption

TABLE OF CONTENTS

SYNOPSIS.....	4
ABBREVIATIONS.....	6
TRIAL / STUDY BACKGROUND INFORMATION AND RATIONALE.....	10
TRIAL / STUDY OBJECTIVES AND PURPOSE	11
PURPOSE	11
PRIMARY OBJECTIVE	11
SECONDARY OBJECTIVES	12
DETAILS OF PRODUCT(S)	12
Description	12
Manufacture	12
Packaging and labelling	12
Storage, dispensing and return	12
Placebo	12
Known Side Effects	12
TRIAL / STUDY DESIGN	13
TRIAL / STUDY CONFIGURATION	13
Primary endpoint	13
Secondary endpoints	13
Safety endpoints	13
Stopping rules and discontinuation	14
RANDOMIZATION AND BLINDING	14
Maintenance of randomisation codes and procedures for breaking code	15
TRIAL/STUDY MANAGEMENT	15
DURATION OF THE TRIAL / STUDY AND PARTICIPANT INVOLVEMENT	15
End of the Trial	15
SELECTION AND WITHDRAWAL OF PARTICIPANTS	15
Recruitment	15
Eligibility criteria	16
Inclusion criteria	16
Exclusion criteria	16

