Two-way analysis of variance (ANOVA) will be used to determine statistically significant differences between the mean baseline and follow-up measurements of all outcomes in both groups. Additionally, the independent samples t-test will be used to compare mean changes in outcomes between the two groups and test for statistical significant differences between them. Non-parametric alternatives will be used if data are non-normally distributed. If, despite randomisation, the mean value of an outcome at baseline is different between the groups then linear regression analysis will be performed to account for the baseline difference. The significance level will be set at $p=0.05$.

Interim analysis of available data will be performed 8-10 months into the course of the study, in order to inform the funding organisation that progress is being made. Finally, in order to maintain the safety of participants, the occurrence of adverse events will be continuously monitored and if an unacceptably high incidence of such events is noted, this will be highlighted to the Chief Investigator and Co-Investigators. At this point, a decision will be made regarding continuation of the study, or if other safety procedures are required to reduce the AE occurrence rate.

Sample size and justification

This is a pilot study, as such, no power calculation has been performed to justify sample size. However, a previous study with similar participant numbers has successfully demonstrated significant improvements in beta-cell function following a HIIT intervention (Madsen *et al.*, 2015b).

Assessment of efficacy

The primary endpoint for this study is pancreatic beta-cell function assessed during an IVGTT. Thus, the HIIT intervention will be deemed efficacious if participants in the intervention group have a significantly higher beta-cell function than those in the control group, i.e. there is a greater improvement in insulin response to intravenous glucose after the 16-week intervention than after 16 weeks of usual care. Significant difference will be determined using two-way ANOVA (or other more appropriate statistical tests) as outlined above.

The secondary endpoints will provide evidence of the efficacy of the HIIT intervention on inducing improvements in other measures of cardiometabolic health and are listed below:

- Improvement in insulin sensitivity suggested by increased insulin sensitivity index (derived from the IVGTT) and reduced HOMA2-IR

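### The efficacy rule treats a higher level and a greater improvement as one thing and leaves open which test decides, so the 5% error rate is not secured

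*Protocol*

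**What the plan says.** All references are to the Protocol.

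- **Statistics, Assessment of efficacy** sets the success rule. HIIT is efficacious "if participants in the intervention group have a significantly higher beta-cell function than those in the control group, i.e. there is a greater improvement". The second half of that condition reads in full "there is a greater improvement in insulin response to intravenous glucose after the 16-week intervention than after 16 weeks of usual care".
- **The same section** names the test: "Significant difference will be determined using two-way ANOVA (or other more appropriate statistical tests) as outlined above".
- **Statistics, Methods**, to which that sentence points back, says that the ANOVA will "determine statistically significant differences between the mean baseline and follow-up measurements of all outcomes in both groups". No term (group, time or interaction) is named as the deciding one, and the ANOVA is not described as repeated-measures. The Synopsis has it testing both within-group and between-group differences.
- **Methods** adds a second test: "the independent samples t-test will be used to compare mean changes in outcomes between the two groups". Non-parametric versions replace these tests if the data are not normal. Linear regression is brought in if an outcome's baseline means differ between the groups, and no threshold for a difference is given.
- **Methods** sets significance at 0.05, without ranking the tests or stating sidedness.
- **Primary objective** words the hypothesis as improvement relative to control, which is a statement about change.

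**The concern.** A difference between arms in level at week 16 and a difference between arms in change are different contrasts. They agree only when the arms start level, which 10 per arm does not ensure. The efficacy sentence treats them as the same, and the sentence after it does not fix which analysis gives the verdict.

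The Protocol declares efficacy by significance, so two things are at stake. If more than one result may count, the chance of calling an ineffective programme efficacious rises above the stated 5%. And if the results differ, nothing in the Protocol says which one stands.

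**Working it through.** **Inputs from the Protocol.** 20 participants allocated 1:1, so 10 per arm (Synopsis); significance level 0.05 (Methods). There is no power calculation to reproduce.

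**Assumptions.** Normal data, SD 1 at both visits, two-sided tests, and a baseline-to-follow-up correlation r that the Protocol does not give, varied over 0.3 to 0.9. There were 40,000 simulated trials per setting, so simulation error is about 0.2 to 0.3 percentage points.

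**Step 1: level and change are not the same contrast.** Take r = 0.7 and n = 10 per arm. The change has SD √(2(1 − r)) = √0.6 = 0.775, and the standard error factor is √(2/10) = 0.447.

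- Baseline difference −0.6 and week-16 difference +0.4: change t = 1.0/(0.775 × 0.447) = 2.89, p = 0.010; level t = 0.4/0.447 = 0.89, p = 0.38.
- Baseline difference +0.7 and week-16 difference +1.0: change t = 0.3/(0.775 × 0.447) = 0.87, p = 0.40; level t = 1.0/0.447 = 2.24, p = 0.038.

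**Step 2: one pair of tests does coincide.** With two visits, the repeated-measures group-by-time interaction F equals the squared t on change. A numerical check gave F = t² = 5.064 and p = 0.0372 for both. If the interaction were the named term, the ANOVA and the change t-test would add no error to each other.

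**Step 3: error rate with no HIIT effect.** Percentage of trials with at least one p < 0.05:

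| Results that may count | r = 0.3 | 0.5 | 0.7 | 0.9 |
|---|---|---|---|---|
| Change t-test alone | 5.0 | 4.9 | 5.0 | 5.0 |
| Week-16 level alone | 5.0 | 5.1 | 4.8 | 4.9 |
| ANCOVA alone | 5.0 | 5.0 | 4.8 | 5.0 |
| Change or ANCOVA | 7.6 | 7.2 | 6.7 | 6.3 |
| Change or level | 8.8 | 9.1 | 9.2 | 9.6 |
| Change, level or ANCOVA | 9.1 | 9.6 | 9.9 | 10.4 |
| The same, or repeated-measures ANOVA group effect | 11.7 | 11.9 | 11.6 | 11.4 |
| The same, or Mann-Whitney on change | 12.3 | 12.3 | 12.1 | 11.9 |

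Over r = 0.3 to 0.8, change or ANCOVA gives 6.6 to 7.6%. Counting only results in favour of HIIT (nominal 2.5%), change or level gives 4.4 to 4.8% over r = 0.3 to 0.9.

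**Step 4: a strict reading of the regression branch.** Suppose only change counts and baseline imbalance means p < 0.05 at baseline (an assumed threshold). If regression then replaces the t-test, the error is 4.2 to 4.7%. If either may then count, it is 4.8 to 5.2% (20,000 trials per setting, r = 0.3 to 0.8).

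**Step 5: what a single baseline-adjusted analysis gains.** The outcome variance is 2(1 − r) for change and 1 − r² for ANCOVA, a ratio of (1 + r)/2: 0.65 at r = 0.3 and 0.85 at r = 0.7. With an assumed true effect of 1 SD, simulated power is 57% for ANCOVA against 43% for the change t-test at r = 0.3, and 82% against 78% at r = 0.7. The cost is one residual degree of freedom (17 instead of 18).

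**The case against.** The strongest reply is that the Protocol intends change. The second half of the efficacy sentence explains the first, the primary hypothesis speaks of improvement, and the only t-test listed is on change. The rank test and the regression are conditional branches, not extra tests run every time. On that reading the error stays near 5% (Step 4). Much of this stands: the inflation arises only if more than one result may count, which the Protocol neither states nor rules out.

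It may also be said that this is a pilot and that a statistical analysis plan could name the ANOVA term. Pilot status explains the absence of a power calculation, but the Protocol still chooses to declare efficacy by significance. A later plan that picked one test would have to narrow a rule that the Protocol itself leaves open.

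Four stronger readings are tempting, and the documents do not support them.

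- **A far larger error rate.** If the two visits were analysed as independent, the ANOVA group effect alone would err in 8.3 to 15.6% of null trials. The Protocol does not specify repeated measures, but neither does it say that the pairing will be ignored.
- **Frequent opposite verdicts when HIIT works.** This sets a stand-alone week-16 t-test against the change t-test, and no such level test is planned.
- **A doubled error rate without qualification.** That holds only if level-type results may count alongside change.
- **Unblinded investigators run the analysis.** Randomization and Blinding and Statistics, Methods both blind staff who work solely on analysis. Supervision is by investigators who cannot be blinded, but the status of the main analyst cannot be determined.

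**Conclusion.** The point holds as a defect in a stated rule: the efficacy sentence merges two contrasts, and the Protocol does not say which result decides. How much error this adds depends on how the rule is read: about 4 to 5% if regression simply replaces the change t-test on significant baseline imbalance, 6.6 to 7.6% if either change or ANCOVA may count, and about 9 to 12% if a level comparison or the ANOVA group effect may count as well. These figures rest on normal data, 10 analysed per arm, two-sided tests and an assumed correlation of 0.3 to 0.8. Any one of the tests, named in advance, keeps 5%. This should be corrected, but it does not undermine the design.

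**What to change.** Name one decisive analysis in Assessment of efficacy: the difference between arms in the 0-10 minute insulin response at week 16, adjusted for its baseline value by linear regression in every case and not triggered by observed imbalance, with a 95% CI. Rewrite the efficacy sentence in those terms and delete the bracketed allowance for other tests. In Methods, label the two-way ANOVA, the change t-test and any rank test as supportive, unable to alter the primary conclusion.

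The cost is two sentences and one degree of freedom. What is given up is the freedom to choose a test after seeing the data.

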In the University of Nottingham Centre Of Metabolism, Ageing & Physiology (COMAP) department, we have developed a novel home-based body-weight HIIT programme. This programme has been previously studied in a group of 18 middle-aged participants for 4 weeks, in comparison to a supervised laboratory HIIT programme and demonstrated similar results between the two groups (Blackwell *et al.*, 2017). This suggests that our home-based programme is as effective at improving cardiovascular fitness as a laboratory-based protocol.

As previously outlined, HIIT has demonstrated positive effects pancreatic beta cell function, and insulin resistance, and deterioration in these parameters, particularly beta cell function is associated with diabetes relapse. We therefore hypothesise that engaging in a HIIT intervention after achieving diabetes remission and being discharged from the Path to Remission programme will prevent the deterioration in beta cell function and insulin resistance. This would suggest that HIIT could improve maintenance of long-term diabetes remission. Thus, we are conducting this pilot study which will be the first of its kind to be performed. The results from this study will form an initial evidence-base regarding use of this intervention in this setting and will be used to inform the possible development of larger studies aimed at determining the real-world application of home-based HIIT programmes for maintenance of diabetes remission.

TRIAL / STUDY OBJECTIVES AND PURPOSE

PURPOSE

The purpose of this study is to determine the effect of a 16-week home-based HIIT intervention on markers of glucose metabolism and glycaemic control in individuals with T2D that have achieved diabetes remission in the NHS Path to Remission Programme. This will be compared against a control group who will not be involved in any exercise intervention (thus will receive usual care).

PRIMARY OBJECTIVE

Objective: To investigate whether a 16-week home-based HIIT intervention will improve beta-cell function in a group of individuals with T2D that have achieved diabetes remission, compared to a control group participating in no exercise intervention

Hypothesis: Participation in the HIIT intervention will elicit significant improvements in beta-cell function compared to not participating in any exercise intervention

SECONDARY OBJECTIVES

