Objective: To determine whether this home-based HIIT intervention will also lead to greater improvements in glycaemic control and insulin sensitivity in these individuals, compared to no exercise intervention

Hypothesis: Participation in the home-based HIIT intervention will result in significantly improved glycaemic control and insulin sensitivity, compared to not participating in any exercise intervention

Objective: To establish the effects of this home-based HIIT intervention, compared to no exercise, on body weight, body composition and cardiorespiratory fitness (VO_{2max}) in these individuals

Hypothesis: Participation in the home-based HIIT intervention will significantly reduce body weight & body fat, whilst also increasing lean mass & VO_{2max} compared to not participating in any exercise intervention

DETAILS OF PRODUCT(S)

This study will not be investigating the physiological effects of any medicinal products. However, one product will be used to assist in measuring some of the outcomes and is described below.

Description

20% glucose solution – this is a solution of dextrose sugar that contains 20g per every 100ml of fluid. This will be administered intravenously to participants during the IVGTT to stimulate an insulin response. This is widely utilised in clinical studies for the calculation of pancreatic beta cell function and insulin sensitivity, as well as in clinical practice to provide care to patients.

Manufacture

20% glucose – Baxter International, USA

Packaging and labelling

The glucose solution is packaged and labelled by the manufacturers prior to purchase and delivery to the research facility.

Storage, dispensing and return

The glucose solution will be stored in a cool, dry area at room temperature, in accordance with the manufacturer's instructions. This area is located within a restricted access section of the research department when only researchers can access. Any solution remaining following use on a study day will be discarded.

Placebo

There will be no placebo for this study.

Known Side Effects

The incidence of side effects to intravenous glucose is very rare. Side effects identified in literature include chills, fever, electrolyte and fluid imbalance, hypersensitivity, localised reaction or pain, rash or venous thrombosis. However, these are very rarely encountered despite glucose being frequently used in clinical practice and clinical studies.

Reference source:

TRIAL / STUDY DESIGN

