- Improvement in overall glycaemic control – reduced HbA1c, reduced fasting glucose, reduced fasting insulin
- Reduced body weight
- Improved body composition – reduced fat mass and increased lean body mass
- Increased muscle strength and muscle function during electromyography, gait and balance analysis

- Increased fascicle length and greater pennation angle in the vastus lateralis muscle (determined by ultrasonography)
- Improved cardiorespiratory fitness – determined by increased VO_{2max} during CPET

Assessment of safety

Safety of participants will be actively monitored throughout the course of the study. Participants will be contacted regularly through the 16-week study to determine occurrence of adverse events. These will be documented in the participant's case report form and in the trial master file. There will also be a database specifically designated to the documentation of adverse events and safety concerns. This database will be reviewed regularly by the Chief Investigator and Co-Investigators. If there is a high occurrence of adverse events then this will be discussed and considerations made about altering the protocol to counteract this. If the occurrence becomes unacceptably high then the study will be terminated before completion.

Procedures for missing, unused and spurious data

This is a small research study, therefore missing data would have a significant impact on the validity of the results obtained. As such, every effort will be made to ensure the amount of missing data is kept to a minimum. Study visits will be performed by researchers who have a full and complete understanding of every aspect of the study. There will be a detailed proforma with clear instructions regarding the data that are to be collected at each timepoint. In addition, any samples requiring storage prior to analysis will be duplicated and stored in separate freezers.

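### The secondary efficacy list names no comparator, within-group tests are planned beside between-group ones, and the protocol does not say which result decides a secondary conclusion

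*Protocol*

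**What the plan says.** **Secondary criteria (Protocol, Statistics, Assessment of efficacy).** The lead-in is "The secondary endpoints will provide evidence of the efficacy of the HIIT intervention on inducing improvements in other measures of cardiometabolic health". The items that follow are directions of the measure itself, for example "Improvement in overall glycaemic control – reduced HbA1c, reduced fasting glucose, reduced fasting insulin" and "Reduced body weight". Body composition, muscle measures and VO2max are handled the same way. No item names the control group.

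**Primary criterion (same section, just above).** This one is comparative: HIIT succeeds if "there is a greater improvement in insulin response to intravenous glucose after the 16-week intervention than after 16 weeks of usual care".

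**Secondary hypotheses (Secondary Objectives).** These are comparative too. HIIT "will result in significantly improved glycaemic control and insulin sensitivity, compared to not participating in any exercise intervention"; the hypothesis on weight, composition and fitness is also set against no exercise.

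**Tests.** The synopsis states: "Outcomes will be tested for significant within-group and between-group differences". Statistics, Methods describes the two-way ANOVA as a comparison of baseline with follow-up means in both groups and does not name the group-by-time interaction. It then adds an independent-samples t-test of mean change between groups for outcomes in general, and linear regression if baseline means differ.

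**Rationale (Background).** Weight regain and relapse are described as the known risk after the diet programme, and the hypothesis is that HIIT "will prevent the deterioration in beta cell function and insulin resistance".

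**The concern.** Randomisation protects the contrast between arms. It does not protect a pre-post change within one arm, which mixes any HIIT effect with whatever would have happened anyway. The secondary list drops the comparator, within-group significance tests are planned, and the protocol does not rank the results, so a secondary claim can go wrong in two ways.

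- **False claim.** A measure that improves in both arms, for example through practice on a repeated test, can show a significant change in the HIIT arm and be reported as supporting HIIT.
- **Missed benefit.** A measure that HIIT keeps stable while controls worsen supports the rationale, but does not show the listed reduction or increase.

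The results are meant to form an initial evidence base and to inform larger studies, so a secondary signal misread in either direction could mislead that decision.

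**Working it through.** **Text comparison**

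| Place | Reference to control? |
|---|---|
| Secondary Objectives, hypotheses | Yes |
| Assessment of efficacy, primary | Yes |
| Assessment of efficacy, secondary list | No |
| Synopsis, tests | Both within-group and between-group |
| Methods, ANOVA sentence | Baseline v follow-up in both groups; interaction not named |
| Methods, t-test of change | Yes, for outcomes in general |

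No sentence says which of the last three results settles a secondary conclusion.

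**Inputs for the illustration.** The protocol gives no effect size, SD or power, so there is no figure to reproduce. From the synopsis: 20 participants, 1:1, hence n = 10 per arm. From Methods: significance level 0.05, taken here as two-sided because the sidedness is not stated. Assumed: normally distributed change scores, the same SD of change in both arms, and the drift sizes below, in units of that SD.

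**Case A: equal improvement d in both arms, no HIIT effect.**
Within-arm paired t-test: df = 9, critical value 2.262, noncentrality d√10.
- d = 0.3: noncentrality 0.949; P(significant improvement in the HIIT arm) = 0.134
- d = 0.5: noncentrality 1.581; P = 0.293

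Probability p(1 − p) that the HIIT arm is significantly improved and the control arm is not:
- d = 0.3: 0.134 × 0.866 = 0.116
- d = 0.5: 0.293 × 0.707 = 0.207

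The between-arm t-test of change has a true difference of 0, so it favours HIIT significantly in 0.05/2 = 2.5% of trials at any d. A simulation of 40,000 trials agrees: 13.5% and 29.5% within arm, 11.7% and 20.9% for the split pattern, and 2.4% between arms.

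**Case B: HIIT arm has no true change, controls worsen by d.**
The HIIT arm shows a significant improvement in 2.5% of trials. If the listed direction is judged on the sign of the mean change alone, it is met in about 50%, which is chance.
Between-arm t-test: df = 18, critical value 2.101, noncentrality d√(10/2).
- d = 0.8: noncentrality 1.789; power 0.39
- d = 1.0: noncentrality 2.236; power 0.56
- d = 1.3: noncentrality 2.907; power 0.78

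In the simulation at d = 1.0, the between-arm test is positive while the HIIT arm shows no significant improvement in 54% of trials.

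**Which outcomes each case fits.** Regain after the diet and regression to the mean after selection on HbA1c below 48 mmol/mol both point to worsening, so weight and HbA1c fit Case B. Case A fits repeat-tested performance measures. The one-repetition-maximum knee extension is scheduled at the first study visit and again at the final visit, and no practice session for it is described. The CPET is preceded by a light familiarisation ride at screening, which may reduce but need not remove learning.

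**The case against.** The strongest reply is that the right test is already planned. Methods applies an independent-samples t-test of change to outcomes in general, with regression if baselines differ, and the synopsis repeats the t-test. The power figures in Case B are the power of that planned test, so they do not measure a loss under the protocol as written. The list can also be read as giving only the favourable direction for each measure, with the comparator supplied by the secondary hypotheses. The only explicit decision rule is for the primary endpoint, and it is comparative.

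Much of this stands. A reader might infer that the protocol defines secondary success as a within-arm change. It does not: no sentence makes a one-arm change sufficient. A reader might also infer that shared drift would produce false reductions in HbA1c or weight. The documents do not support that either, because the drift they describe for those measures is deterioration.

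Two things remain. The list omits the comparator that the adjacent primary criterion states, and the protocol authorises within-group and between-group tests without saying which governs secondary conclusions. Detail can be left to an SAP, but the mismatch is in what the protocol itself says. The tension with prevention of deterioration is softer, since that phrase is in the background while the formal hypotheses speak of improvement. Even so, those hypotheses are comparative, and improvement relative to control includes holding steady while controls decline.

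**Conclusion.** The concern holds as an inconsistency and an unresolved choice about secondary endpoints, not as an error in a stated figure and not as a plan that relies only on within-group evidence. The missed-benefit risk has the firmer basis, because the background expects deterioration without intervention. The false-claim risk is plausible mainly for strength and CPET measures.

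If a secondary claim were rested on the within-arm test, the chance of a false finding for HIIT would be about 13% to 29% for an assumed shared improvement of 0.3 to 0.5 SD of change, against 2.5% for the between-arm test. These figures assume 10 complete pairs per arm, normal changes with equal SD, and drift sizes that the documents do not give. They show scale and are not a forecast for this trial. The point is worth correcting because the remedy uses data already collected.

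**What to change.** 1. In Assessment of efficacy, preface the secondary list with: *Evidence for each secondary endpoint is the HIIT-minus-control difference at week 16, adjusted for baseline, with 95% CI, in the direction listed.*
2. In the synopsis, remove the reference to within-group testing.
3. In Methods, align the ANOVA sentence with this contrast, so that it no longer reads as a baseline v follow-up test in each group.
4. Report within-arm mean changes descriptively, without p-values.

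**Cost.** This is a small analysis change, not wording only: routine baseline adjustment replaces the regression that Methods makes conditional on a baseline difference. It spends one degree of freedom (17 instead of 18 residual with 20 complete participants), and fewer p-values are reported. No extra data are needed.
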